4 TRIAL DESIGN

A parallel group design where each group of participants receives only one of the study treatments. The participants will be randomised to one of two groups of 50 participants each. One group will receive the Rheumatoid Arthritis information booklet at screening and both groups will have blood taken for RC-MTX polyglutamate levels at screening and 3 – 6 months later, the group who did not receive the booklet will receive the Rheumatoid Arthritis information booklet when they return 3 – 6 months later. Following a peer review of the protocol, participants who have to stop taking Methotrexate due to eg infection or abnormal blood laboratory result, will be able to continue in the study provided they have been on their original stable dose of MTX for at least 4 weeks prior to taking the second blood tests.

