Educating patients about the drug and why they are taking it has been shown to improve adherence (Quinlan 2009) “The finding that health knowledge, especially medication knowledge, is influenced by health literacy, age, income and education”. Chugai/Roche have recently produced a booklet for people who have Rheumatoid Arthritis (Chugai/Roche 2014a). This has been designed with psychology input to prompt the patients to think about and then assess using a scale from 0 – 10 how their treatment suits them across 7 domains. These domains reflect drug use, efficacy, side effects and drug concerns. A low score in a domain prompts the user to turn to a certain section in the booklet for more information. A pilot study of the booklet has shown it to be well received and useful to patients (Chugai/Roche 2014b).

Measuring adherence is also a problem as patients may not be entirely open about how they take their drugs. Questionnaires have been used, but we suspect from talking to patients and health care professionals, that, who delivers the questionnaire and how it is delivered may make a difference to responses. Methotrexate is quickly cleared from the blood, but metabolites known as polyglutamates collect in the red cells (RC-polyglutamates) and give a longer look at drug taking. We plan to measure these for comparison with the Methotrexate dose and the adherence data.

Benefits of the Study to the NHS

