3.3.2 Secondary endpoints/outcomes

The secondary outcome measure is the measurement of RC-MTX polyglutamate levels in a venous blood sample at two timepoints from all study patients to detect if Methotrexate Adherence correlates with RC-MTX polyglutamate levels.

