6 ELIGIBILITY CRITERIA

6.1 Inclusion criteria

- Subjects capable of giving informed consent in English
- Male or female
- Over the age of 18 years

- Diagnosis of Rheumatoid Arthritis
- On a stable dose of Methotrexate for at least 3 months

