8.2 Statistical analysis plan

Sample size estimation

This is a pilot study, and as such key outcomes of interest relate to recruitment rates, drop outs a/loss to follow up and data quality and missing data for completion of the adherence questionnaire. We will also collect data on change in adherence with medication and change in polyglutamate levels in red blood cells from baseline to follow-up in each group. This will help inform a sample size calculation for a fully powered clinical trial. For an external pilot study designed to establish the sample size for a definitive randomised controlled trial, with a normally distributed continuous primary clinical outcome, Teare, et al¹ recommend a minimum sample size in each group of 35. To allow for a maximum drop-out rate of 30% at follow-up, we aim to recruit 50 subjects per group (100 in total).

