8.4 Subject population

The subject population under study are patients with Rheumatoid Arthritis over the age of 18 and who have been on a continuous stable dose of Methotrexate for at least 3 months.

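### The second polyglutamate sample may follow only 4 weeks back on methotrexate, against 3 months for the first, and the withdrawal criteria contradict the rule that allows this

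*Protocol*

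**What the plan says.** **The interruption rule.** Protocol section 4 states that "participants who have to stop taking Methotrexate due to eg infection or abnormal blood laboratory result, will be able to continue in the study", on the condition "provided they have been on their original stable dose of MTX for at least 4 weeks prior to taking the second blood tests". It gives no maximum length for the break and no reason for choosing 4 weeks, beyond saying that the rule followed peer review.

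**The entry rule.** Section 6.1 requires participants to be "On a stable dose of Methotrexate for at least 3 months". Section 8.4 describes the population as patients "who have been on a continuous stable dose of Methotrexate for at least 3 months".

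**The withdrawal rule.** Section 7.6 lists stopping methotrexate, or a change from the stable dose, among the grounds for withdrawal. It makes no exception for the participants whom section 4 keeps.

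**What the assay is for.** Section 1 explains that "metabolites known as polyglutamates collect in the red cells (RC-polyglutamates) and give a longer look at drug taking". Under section 4, "both groups will have blood taken for RC-MTX polyglutamate levels at screening and 3 – 6 months later". Section 3.3.2 uses the two levels "to detect if Methotrexate Adherence correlates with RC-MTX polyglutamate levels". Section 8.2 collects "change in polyglutamate levels in red blood cells from baseline to follow-up in each group" to help size a later definitive trial.

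**The concern.** The assay is valued because it looks back over a longer period, so a recent break may still show in it. The first sample is taken after at least 3 months on a stable prescribed dose. The second may come 4 weeks after a break of any length that fits between the visits. For those participants the two samples need not reflect the same prescribed exposure, and part of any fall may belong to the break and not to the participant's behaviour.

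Two results are exposed. One is the correlation between reported adherence and level. The other is the change in level and its spread, which the pilot is meant to estimate for the next trial.

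The problem arises only if these participants stay in. Section 4 says they do and section 7.6 says they do not, so the protocol does not settle who supplies a second sample. It also leaves unclear who counts as a drop-out, which section 8.2 names as a key pilot outcome.

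**Working it through.** **Plan's own figure.** The only stated calculation is the sample size in section 8.2: 35 per group with 30% drop-out gives 35 / 0.70 = 50 per group, 100 in total. It reproduces and is not affected by this point. The protocol states no figure for assay kinetics.

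**Inputs from the protocol**
- Minimum time back on drug before the second sample: 4 weeks (section 4).
- Time on a stable dose before the first sample: at least 3 months, about 13 weeks (sections 6.1 and 8.4).
- Interval between samples: 3 to 6 months, about 13 to 26 weeks (section 4). The longest break that still allows 4 weeks back on drug is therefore 13 − 4 = 9 weeks for a 3-month interval and 26 − 4 = 22 weeks for a 6-month interval.

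**Assumptions, because the protocol gives no figures**
- First-order build-up and loss, with the patient at steady state before the break.
- Half-life h from 1 to 8 weeks.
- Length of break L from 1 to 22 weeks.
- Every prescribed dose is taken before and after the break.

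**Formula.** With t weeks back on drug, the level as a share of the patient's own previous level is

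level = 1 − (1 − 2^(−L/h)) × 2^(−t/h)

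Example with h = 4, L = 4, t = 4: 1 − (1 − 0.5) × 0.5 = 0.75.

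**Results at t = 4 weeks (% of previous level)**

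| Half-life (weeks) | 1 week off | 2 weeks off | 4 weeks off | 9 weeks off | 22 weeks off |
|---|---|---|---|---|---|
| 1 | 96.9 | 95.3 | 94.1 | 93.8 | 93.8 |
| 2 | 92.7 | 87.5 | 81.2 | 76.1 | 75.0 |
| 3 | 91.8 | 85.3 | 76.1 | 65.3 | 60.6 |
| 4 | 92.0 | 85.4 | 75.0 | 60.5 | 51.1 |
| 6 | 93.1 | 87.0 | 76.7 | 59.3 | 42.0 |
| 8 | 94.1 | 88.7 | 79.3 | 61.7 | 39.8 |

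The fall is about 3–15% for breaks of 1 to 2 weeks. For breaks of 4 to 9 weeks it is about 19–41% if the half-life is 2 weeks or more. With a half-life of 1 week it never exceeds about 6%.

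**Comparison at t = 13 weeks.** For half-lives of 1 to 8 weeks the level is 100.0% down to 90.5% after 4 weeks off, and 100.0% down to 82.4% after 9 weeks off. Three months back on drug shrinks the gap but does not always close it.

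**Effect on a group mean.** The number affected is unknown. If 10% of a group were affected (assumed) and their levels were 60% to 85% of baseline, the group mean would fall by 0.10 × 0.40 = 4% to 0.10 × 0.15 = 1.5%.

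**Data capture.** Section 7.1 asks at recruitment how long the current dose has been taken, and section 7.4 asks when methotrexate was first prescribed. The schedule in Appendix 4 includes concomitant medication. None of these asks for stop and restart dates of a break between the two samples, and section 9.1 confines the CRF to data that the protocol requires.

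**The case against.** The strongest objection is that section 7.6 already removes these participants, so the harm may never arise. That stands as a condition: the distortion occurs only if section 4 prevails. It does not dispose of the point, because the contradiction is itself a fault in the protocol.

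A second objection is that flagging and sensitivity analyses belong in a SAP, which is not shown. This is fair for the analysis detail. But the 4-week rule is fixed in the protocol, and no analysis plan can flag breaks whose dates were not collected. The CRF is not shown either, and someone applying the 4-week rule must learn the restart date. No listed data item requires it to be recorded.

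Third, the 4-week rule is itself a safeguard added after peer review, and the protocol never says that the 3-month entry rule was set to reach assay steady state. Both statements are correct. The comparison shows unequal exposure. It does not show that 4 weeks is wrong.

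A reader might also infer more than the documents support:
- *That a fully adherent patient would be classed as non-adherent.* No polyglutamate level defines non-adherence, so no such classification exists.
- *That the correlation must be biased towards zero.* The questionnaire is not in the documents. If a directed break is scored as good adherence, low levels pair with good scores and the correlation weakens. If it is scored as missed doses, low levels pair with low scores and it need not.
- *That these samples will be analysed like all the others.* The protocol is silent on this.

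**Conclusion.** The point holds in conditional form. Sections 4 and 7.6 contradict each other and must be reconciled. If interrupted participants stay in, their two samples can reflect unequal prescribed exposure, so a fall in level is not a clean sign of adherence.

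The size for an individual depends on an assumed half-life and an unknown length of break: small for short breaks or a half-life near 1 week, material for breaks of several weeks with a half-life of 2 weeks or more. The effect on group results also depends on how many are affected.

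The consequence is limited to the polyglutamate analyses of a largely descriptive pilot. The questionnaire outcomes are not measured by this assay. It should still be corrected, because the remedy is cheap and the dates may be hard to recover later.

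**What to change.** 1. Reconcile sections 4 and 7.6, so that it is clear who stays in the study and who supplies a second sample.
2. Require stop and restart dates for every methotrexate interruption between the two samples.
3. Flag second samples with an interruption in the preceding 3 months, which matches the length of the entry requirement. Report the adherence-level correlation with and without flagged samples, or adjusted for weeks on drug. The flag is not a clean threshold: at a 3-month visit it catches any break on study, however brief, and with a long half-life some shortfall remains after 13 weeks.
4. Keep all randomised participants in the between-arm analysis of change. Leave flagged samples out only in a sensitivity analysis, because an interruption occurs after randomisation and excluding on it could unbalance the arms.

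The cost is two date fields, a little more analysis, and somewhat fewer samples in one version of a secondary analysis. No change to any treatment or restart decision is proposed.

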5 STUDY SETTING

This will be a single centre study in a secondary care setting. No PIC sites will be used. Potential participants will be invited to take part in the study when they attend for their routine Methotrexate blood monitoring. All potential study subjects will be approached first by the clinical team and then referred to the researcher if they are interested in taking part in the study. All interested potential participants will be given the study Patient Information Sheets. The study team will ensure that potential participants have as much time as they need to decide whether to take part in the study, and will be available to answer any questions. However subjects can be consented on the same day if they and the study team feel that they have had sufficient time to make an informed decision to take part.

6 ELIGIBILITY CRITERIA

6.1 Inclusion criteria

- Subjects capable of giving informed consent in English
- Male or female
- Over the age of 18 years

- Diagnosis of Rheumatoid Arthritis
- On a stable dose of Methotrexate for at least 3 months

6.2 Exclusion criteria

- Subjects who are unwilling or unable to take Methotrexate
- Subjects who are unwilling or unable to return for their Methotrexate blood monitoring 3 – 6 months later
- Subjects who are unable to read the Rheumatoid Arthritis booklet or the Methotrexate Adherence and Rheumatoid Arthritis Knowledge Questionnaire.
- Subjects who are unable to read English

7 TRIAL PROCEDURES

7.1 Recruitment

Potential study participants will be recruited at their routine Methotrexate blood monitoring clinic having been identified by the clinical team first. Potential participants will be given a Patient Information Leaflet describing the study, which will describe “Methotrexate Management” rather than “Methotrexate Adherence”. Using the word “Adherence” may affect the way the participants take their medication in order to be compliant with Methotrexate whilst on the study and we wish to avoid that bias. A diagnosis of Rheumatoid Arthritis will be determined by consulting the patients’ notes with their consent. All data collected on the study will be anonymised and each participant will be given a unique study number for identification and safety.

The following data will be collected:

- age
- gender
- ethnicity
- Dose of Methotrexate
- How long on this dose
- Route of administration

- Day of the week Methotrexate is taken
- Other concomitant medication

7.2 Consent

The Chief Investigator (CI) will retain overall responsibility for the informed consent of participants at their site and will ensure that any person delegated responsibility to participate in the informed consent process is duly authorised, trained and competent to participate according to the ethically approved protocol, principles of Good Clinical Practice (GCP) and Declaration of Helsinki. If delegation of consent is acceptable then details will be provided.

Informed consent will be obtained prior to the participant undergoing any study specific procedures.

The right of a participant to refuse participation without giving reasons will be respected.

The participant will remain free to withdraw at any time from the study without giving reasons and without prejudicing his/her further treatment and will be provided with a contact point where he/she may obtain further information about the trial.

There will be:

- discussion between the potential participant or his/her legally acceptable representative and an individual knowledgeable about the research about the nature and objectives of the trial and possible risks associated with their participation
- the presentation of written material e.g., information leaflet and consent document which has been approved by the REC and be in compliance with GCP, local regulatory requirements and legal requirements
- the opportunity for potential participants to ask questions
- assessment of capacity. For consent to be ethical and valid in law, participants must be capable of giving consent for themselves. A capable person will:
 - understand the purpose and nature of the research
 - understand what the research involves, its benefits (or lack of benefits), risks and burdens
 - understand the alternatives to taking part
 - be able to retain the information long enough to make an effective decision
 - be able to make a free choice

- be capable of making this particular decision at the time it needs to be made

7.2.1 Additional consent provisions for collection and use of participant biological specimens

- all biological specimens will be acquired and stored during the trial.
- biological specimens will be used for submission to ethically approved research tissue banks for future specified or unspecified research
 - participants may opt out but still participate in the main study
 - consent for the use of their data and specimens to be stored for further research will be required
 - consent for use in future research unrelated to the clinical condition under study

7.3 The Randomisation Scheme

A block randomisation schedule will be generated by:

Sealed Envelope Ltd. 2016.

<https://www.sealedenvelope.com/simple-randomiser/v1/lists>

7.4 Baseline Data

The following data will be collected at baseline:

- Age in years
- Gender
- Ethnic Origin
- Dose of Methotrexate the subject is currently taking
- Route of Administration
- Date the subject was first prescribed Methotrexate
- Medical history
- Concomitant Medication

7.5 Study Assessments

- Baseline and follow up Methotrexate Adherence questionnaire
- Baseline and follow up Rheumatoid Arthritis knowledge questionnaire
- Two blood test for RC-MTX polyglutamate levels

7.6 Withdrawal criteria

Participants will be withdrawn from the study if:

- They withdraw consent
- Stop taking Methotrexate or change their stable dose
- Are unable to return to clinic for their routine 3 – 6 month blood monitoring appointment
- In the PI's opinion it is in the best interests of the participant to withdraw from the study

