1 BACKGROUND

The aim of this study is to explore any effect of the Rheumatoid Arthritis information booklet (Chugai/Roche 2014a) on the disease management and drug adherence of patients with Rheumatoid Arthritis (RA) taking Methotrexate. We also wish to explore the usefulness of red cell glutamate levels in determining Methotrexate Adherence levels.

Methotrexate is the default disease modifying drug (DMARD) for treatment of RA. It is a drug which has a delayed onset of action and where the majority of patients, even those continuing on treatment, have side effects that they tolerate in order to stay on the drug (Walker et al 2014). Poor drug adherence can give the impression that the therapy has failed which could lead to an economic impact (O’Niell 2011).

The definition of adherence is not straightforward, Haynes et al (2002), describe it as “the extent to which a person’s behaviour coincides with medical or health advice” or Kelly (1995) who suggests “following medical advice sufficiently to achieve the therapeutic goal’. We think that patients can be divided into “Non Adherence”: those patients who stop their prescriptions completely and do not pick up repeat prescriptions; Partial adherence, divided into those who partially adhere but whose disease is under good control; and those who miss medications often enough for their disease not to be under good control.

The reasons for incomplete adherence are only partly understood. They may relate to the tolerance problems (Hill 2005). Some patients find adhering to medication regimes a chore (Duerden 2013). Understanding why they are taking the drugs has been shown to improve adherence (Hill 2005). Jackson (2014) has divided the reasons into Capability; Opportunity and Motivation.

A World Health Organisation survey of a long term drug use indicates that as many as 40% of patients do not take their prescriptions as intended (2003). Patients have admitted to us of not always taking the Methotrexate and to taking a “Methotrexate holiday” when they can’t face taking it (Walker et al 2014). They are often reluctant to divulge this to the healthcare staff they see. There are many reasons for this ranging from embarrassment, not wanting to “upset” their health care provider to fearing that their drugs may be stopped.

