3 OBJECTIVES AND OUTCOME MEASURES/ENDPOINTS

3.1 Primary objective

The primary objective of this project is to determine if a Rheumatoid Arthritis information booklet increases understanding of Rheumatoid Arthritis in patients with this disease and leads to better disease management through drug adherence.

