3.3 Outcome measures

3.3.1 Primary endpoint/outcome

The primary outcome measure is the responses to the Methotrexate Adherence and the Rheumatoid Arthritis Knowledge questionnaires. Subjects will be randomised 50:50 to receive the Rheumatoid Arthritis information booklet. Those participants who do not receive the booklet at randomisation will receive it 3 – 6 months later when the participant returns for their routine Methotrexate blood monitoring appointment. The aim of this is to determine whether the intervention of the Rheumatoid

Arthritis information booklet has an impact on patient Methotrexate management. All patients will be given the Methotrexate Adherence questionnaire and the RA Questionnaire at screening and again 3 – 6 months later.

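### Section 7.6 withdraws participants who stop methotrexate, which cuts off the worst end of the adherence outcome after randomisation and does not agree with Section 4

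*Protocol*

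**What the plan says.** Section 7.6 opens with "Participants will be withdrawn from the study if", and its second bullet reads "Stop taking Methotrexate or change their stable dose". It gives no reason, duration or exception, and the consequence is leaving the study, not only an analysis set. The third bullet withdraws anyone who cannot return for the routine 3–6 month monitoring appointment.

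Section 4 says that "participants who have to stop taking Methotrexate due to eg infection or abnormal blood laboratory result, will be able to continue in the study". The condition is that they have been back on the original stable dose for at least 4 weeks before the second blood tests. Neither section refers to the other.

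The Background describes the non-adherent as "those patients who stop their prescriptions completely and do not pick up repeat prescriptions". It treats partial adherence as a separate category with two kinds: patients whose disease is well controlled, and "those who miss medications often enough for their disease not to be under good control".

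The primary objective (Section 3.1) asks whether the booklet "leads to better disease management through drug adherence". Section 3.3.1 states: "The primary outcome measure is the responses to the Methotrexate Adherence and the Rheumatoid Arthritis Knowledge questionnaires". Both questionnaires are due from all patients at screening and 3–6 months later. The secondary outcome (Section 3.3.2) is whether adherence correlates with red-cell polyglutamate levels. Section 8.2 names drop-out and loss to follow-up among the key pilot outcomes.

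**The concern.** A participant who gives up methotrexate after randomisation has the clearest form of non-adherence that the protocol recognises. Section 7.6 removes that person before the follow-up questionnaires. The adherence comparison is then made among people selected on part of the outcome.

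The selection may differ by arm. The booklet asks patients to score domains that reflect drug use, efficacy, side effects and drug concerns, and "A low score in a domain prompts the user to turn to a certain section in the booklet for more information". It is plausible, though not shown, that such prompting changes whether a patient stops, in either direction.

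Three things are at stake:

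- The level of non-adherence, and any booklet effect that works through stopping, would be misestimated. Section 8.2 wants change in adherence to inform a definitive trial.
- An adherence event would be counted as drop-out, so the pilot could not separate the two.
- The lowest adherence values would be missing from the correlation with polyglutamates.

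Separately, a participant who has a required, temporary stop is kept under Section 4 and withdrawn under Section 7.6.

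**Working it through.** **Plan's own figure.** Section 8.2 takes a minimum of 35 per group and a maximum drop-out of 30%: 35 / (1 − 0.30) = 50 per group, 100 in total. This reproduces and is not disputed. The protocol does not say whether the 30% includes withdrawals under this rule. If it does, 50 × 0.70 = 35 per group remain. If stopping came on top of a full 30% of other losses, 50 × (1 − stop) × 0.70 gives about 33 at 5% stopping, 31.5 at 10% and 28 at 20%.

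**Does the rule touch the outcome?** Section 7.6 withdraws those who stop. The Background calls complete stopping non-adherence. Sections 3.1 and 3.3.1 make adherence part of the primary objective and outcome, measured again at 3–6 months. So the rule removes one of the protocol's own adherence categories before that measurement. Participants who miss doses without stopping are not caught.

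**How large could the effect be?** The protocol gives no methotrexate stopping rate, so every rate below is an assumption. Let *s* be the proportion who stop and *p* the proportion who are partially non-adherent, both out of all randomised in the arm.

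- True non-adherence = s + p
- Observed after withdrawal of stoppers = p / (1 − s)

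| Case | s control / booklet | p control / booklet | True (difference) | Observed (difference) |
|---|---|---|---|---|
| a | 15% / 5% | 30% / 30% | 45% v 35% (10) | 0.30/0.85 = 35.3% v 0.30/0.95 = 31.6% (3.7) |
| b | 10% / 5% | 30% / 30% | 40% v 35% (5) | 0.30/0.90 = 33.3% v 31.6% (1.8) |
| c | 20% / 10% | 20% / 20% | 40% v 30% (10) | 0.20/0.80 = 25.0% v 0.20/0.90 = 22.2% (2.8) |
| d | 5% / 5% | 30% / 30% | 35% v 35% (0) | 31.6% v 31.6% (0) |
| e | 10% / 10% | 30% / 20% | 40% v 30% (10) | 33.3% v 22.2% (11.1) |

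In a to c the arms differ only in stopping, and a true 5–10 points is observed as 1.8–3.7. In d the difference is unaffected but the level falls from 35% to 31.6%. In e, where the booklet acts only on partial adherence, the observed difference is slightly too large. The level is understated in all five cases.

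**Alternative assumption.** Suppose instead that the continuers are alike, with the same partial rate *q* among continuers in each arm. The observed difference is then q − q = 0. The true difference is (s control − s booklet) × (1 − q). For gaps in stopping of 5–10 points, that is 5–10 points at q = 0 and 3.5–7 points at q = 30%.

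**Section 4 against Section 7.6.** Take a participant told to stop because of an infection, who resumes the original dose and has been on it for at least 4 weeks by the second blood tests. Section 4 keeps this person; the second bullet of Section 7.6 withdraws the same person. Someone who stops by choice is not covered by Section 4, so the two sections do not conflict there.

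**The case against.** The strongest reply has five parts.

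- **The outcome survives.** A reader might infer that the rule deletes the adherence outcome. It does not. Partial adherers stay in and are measured, as are patients who conceal that they have stopped. This stands: the outcome is truncated at one end.
- **The effect need not vanish.** A reader might infer that any booklet effect through stopping is observed as nothing. That holds only if the continuers are alike in both arms; other assumptions shrink the difference, and case e enlarges it. An imbalance in stopping would also appear in drop-out counts by arm, mixed with other losses. This stands, and is why the size is given as a range.
- **Section 4 can be read as a specific exception to a general rule.** It follows a peer review and covers only required stops with a return to the original dose. That limits the conflict to those participants. It does not remove it, because Section 7.6 mentions no exception.
- **A stable dose has a purpose.** The Background and Section 2 compare polyglutamate levels with the prescribed dose, so a dose condition plausibly serves the blood endpoint. Clinician-directed dose changes are also not non-adherence. Both points stand, but neither is a reason to lose the questionnaires.
- **This is a pilot with mainly descriptive analysis (Section 8.3).** True, but drop-out and change in adherence are what it is meant to estimate, and Section 8.3 allows inferential tests for effect size.

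A reader might also re-inflate the 35 per group for a smaller drop-out and conclude that the definitive trial would be oversized. The protocol does not support that: 35 is the minimum for the pilot, and the 30% is an allowance, not a forecast.

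**Conclusion.** The point holds as a truncation of the adherence outcome and a limited inconsistency between Sections 4 and 7.6. It rests on the text and does not depend on the assumed rates. The rule ends participation after randomisation for a category that the protocol itself calls non-adherence, and an analysis plan cannot recover questionnaires that were never collected.

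The size is uncertain because no stopping rate is given. With assumed stopping of 10–20% in controls and 5–10% with the booklet, a true 5–10 point difference shrinks to about 2–4 points when partial non-adherence is equal among all randomised. The observed difference is 0 when continuers are alike. With equal stopping, the level of non-adherence is still understated. The recruitment target of 50 per group is arithmetically correct and needs no change on this account, provided the 30% allowance is meant to include these withdrawals.

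**What to change.** Separate stopping or changing methotrexate from leaving study follow-up:

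- Replace the second bullet of Section 7.6 with a recorded event: date, reason, and whether it was the patient's choice or clinician-directed.
- Still collect both 3–6 month questionnaires from these participants, and keep them in their allocated arm for the questionnaire outcomes.
- Let any requirement for a stable dose limit only the polyglutamate analysis.
- Count patient-chosen stopping as non-adherence; report clinician-directed interruptions and dose changes separately.
- Amend the third bullet so that missing the monitoring appointment does not by itself end questionnaire follow-up. Otherwise it may remove the same people.
- Reconcile Sections 4 and 7.6, with a cross-reference. This concerns study participation and data collection only; no treatment decision changes.

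The cost is amendment wording and a CRF field. Someone who has stopped may no longer attend methotrexate monitoring, and Appendix 1 ties study blood to those appointments, so postal or telephone questionnaires may be needed. No increase in sample size follows.
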